9.4.2 Calculation or derivation of safety variables

9.4.2.1 Adverse events

Safety and tolerability will be assessed in terms of AEs (including SAEs), deaths, laboratory data, vital signs, ECGs, and exposure. These will be collected for all participants. Data from all cycles of treatment will be combined in the presentation of safety data. "On treatment" will be defined as assessments between date of start dose and 90 days following discontinuation of IP (ie, the last dose of durvalumab monotherapy or placebo). For AEs, on treatment (or treatment-emergent AEs) will be defined as any AEs that started after dosing or prior to dosing and which worsens following exposure to the treatment.

AEs observed up until 90 days following discontinuation of IP or until the initiation of the first subsequent therapy following discontinuation of treatment (whichever occurs first) will be used for the reporting of the AE summary tables. This will more accurately depict AEs attributable to study treatment only, as a number of AEs up to 90 days following discontinuation of treatment are likely to be attributable to subsequent therapy. However, to assess the longer-term toxicity profile, AE summaries will also be produced containing AEs observed up until 90 days following discontinuation of IP (ie, without taking subsequent therapy into account). Any events in this period that occur after a participant has received further therapy for cancer (following discontinuation of study treatment) will be flagged in the data listings.

The SAS will be used for reporting of safety data.

A separate data listing of AEs occurring more than 90 days after discontinuation of IP will be produced. These events will not be included in AE summaries.

Any AE occurring before treatment with study treatment will be included in the data listings but will not be included in the summary tables of AEs.

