8.3.1 Method of detecting adverse events and serious adverse events

Care will be taken not to introduce bias when detecting AEs and/or SAEs. Open-ended and non-leading verbal questioning of the participant is the preferred method to inquire about AE occurrences.

8.3.2 Time period and frequency for collecting adverse event and serious adverse event information

AEs and SAEs will be collected from the time of the participant signing the ICF of study procedure (part II screening) until the Follow-up Period is completed (90 days after the last dose of study drug). If an event that starts post the defined safety Follow-up Period noted above is considered to be due to a late onset toxicity to study drug, then it should be reported as an AE or SAE as applicable.

All SAEs will be recorded and reported to the Sponsor or designee within 24 hours, as indicated in Appendix B. The Investigator will submit any updated SAE data to the Sponsor within 24 hours of it being available.

Investigators are not obligated to actively seek AEs or SAEs in former study participants. However, if the Investigator learns of any SAE, including a death, at any time after a participant's last visit and he/she considers the event to be reasonably related to the study treatment or study participation, the Investigator should notify the Sponsor.

The method of recording, evaluating, and assessing causality of AE and SAE and the procedures for completing and transmitting SAE reports are provided in Appendix B.

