8.3.12 Deaths

All deaths that occur during the study Treatment Period, or within the protocol-defined Follow-up Period after the administration of the last dose of study drug, must be reported as follows:

- Death clearly resulting from disease progression should be documented in the eCRF in the Statement of Death page. It should not be reported as an SAE.
- Where death is not due (or not clearly due) to progression of the disease under study, the AE causing the death must be reported as an SAE within 24 hours. It should also be documented in the Statement of Death page in the eCRF. The report should contain a

comment regarding the co-involvement of PD, if appropriate, and should assign main and contributory causes of death.

• Deaths with an unknown cause should always be reported as an SAE, and documented in the Statement of Death page in the eCRF, but every effort should be made to determine a cause of death. A post mortem may be helpful in the assessment of the cause of death, and if performed, a copy of the post-mortem results should be forwarded to AstraZeneca Participant Safety or its representative within the usual timeframes.

Deaths occurring after the protocol-defined safety Follow-up Period after the administration of the last dose of study drug should be documented in the Statement of Death page. If the death occurred as a result of an event that started after the defined safety Follow-up Period and the event is considered to be due to a late onset toxicity to study drug, then it should also be reported as an SAE.

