All reported AEs will be listed along with the date of onset, date of resolution (if AE is resolved) and investigator's assessment of severity and relationship to durvalumab/placebo/

CRT. Frequencies and percentages of patients reporting each PT will be presented (i.e. multiple events per patient will not be accounted).

AEs that have missing causality (after data querying) will be assumed to be related to study drug.

A separate data listing of AEs occurring more than 90 days after discontinuation of IP will be produced. These events will not be included in AE summaries, unless otherwise stated.

Any AE occurring before treatment with IP will be included in the data listings but will not be included in the summary tables of AEs, unless otherwise stated.

Summary information (the number and percent of patients by system organ class (SOC) and PT separated by treatment group) will be tabulated for:

- All AEs (at patient level, and by event rate)
- All AEs causally related to durvalumab/placebo (as determined by the reporting investigator)
- AEs by maximum reported CTCAE grade
- AEs with CTCAE grade 3 or 4
- AEs with CTCAE grade 3 or 4, causally related to durvalumab/placebo (as determined by the reporting investigator)
- AEs with maximum CTCAE grade 3 or 4
- AEs with maximum CTCAE grade 3 or 4, causally related to durvalumab/placebo (as determined by the reporting investigator)
- Most common AEs
- AEs with outcome of death
- AEs with outcome of death causally related to durvalumab/placebo (as determined by the reporting investigator)
- All SAEs
- All SAEs causally related to durvalumab/placebo (as determined by the reporting investigator)
- AEs leading to discontinuation of durvalumab/placebo
- AEs leading to discontinuation of durvalumab/placebo, causally related to durvalumab/placebo (as determined by the reporting investigator)
- Other significant AEs
- Most common AEs with CTCAE grade 3 or higher
- AEs leading to dose delay of durvalumab/placebo

- AEs from start of first subsequent therapy until 90 days following discontinuation of study treatment
- AEs which started prior to first dose or after 90 days following date of last dose

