 - AE onset prior to subsequent therapy. Which includes AEs with an onset date (or pre-treatment AEs that increase in severity) on or after the date of first dose and up to and including 90 days following the last dose of study medication (durvalumab/placebo), or AE start date \leq the date of initiation of the first subsequent therapy (whichever occurs first).
- Death after end of safety follow up period (last dose of study medication (durvalumab/placebo) + 90 days) and not due to disease under investigation
- COVID-19 related death
- Unknown reason for death
- Other deaths

This summary will be repeated for all deaths on-treatment or within 90 days of last dose of durvalumab/placebo.

Adverse events of special interest and possible interest

Preferred terms used to identify adverse events of special interest and possible interest (as defined in [section 3.3.1](#)) will be listed before DBL and documented in the Study Master File. Grouped summary tables of certain MedDRA preferred terms will be produced and may also show the individual preferred terms which constitute each AESI/AEPI grouping. Groupings will be based on preferred terms provided by the medical team prior to DBL, and a listing of the preferred terms in each grouping will be provided.

An overall summary will include the number and percentage of patients with:

- Any AESI/AEPI (*)
- Any AESI/AEPI, causally related to durvalumab/placebo (*)
- Any AESI/AEPI of CTCAE grade 3 or 4
- Any AESI/AEPI of CTCAE grade 3 or 4, causally related to durvalumab/placebo
- Any AESI/AEPI with outcome of death
- Any AESI/AEPI with outcome of death, causally related to durvalumab/placebo

- Any serious AESI/AEPI (*)
- Any serious AESI/AEPI, causally related to durvalumab/placebo
- Any AESI/AEPI leading to discontinuation of durvalumab/placebo (*)
- Any AESI/AEPI leading to discontinuation of durvalumab/placebo, causally related to durvalumab/placebo
- Any AESI/AEPI leading to dose delay of durvalumab/placebo
- Any AESI/AEPI leading to concomitant medication (*)
- Any AESI/AEPI leading to concomitant medication use (steroids) (*)
- Any AESI/AEPI leading to concomitant medication use (high dose steroids) (*)
- Any AESI/AEPI leading to concomitant medication use (endocrine therapy) (*)
- Any AESI/AEPI leading to concomitant medication use (other immunosuppressants) (*)

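### Late-onset toxicities that sites must report after day 90 enter no related-SAE, related-fatal-AE or AESI/AEPI count, and the one AE table that holds them pools them with pre-dose events

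*Protocol*

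**What the plan says.** **Reporting.** Protocol 8.3.2 collects AEs and SAEs from part II consent to 90 days after the last dose. If a later event is considered "due to a late onset toxicity to study drug, then it should be reported as an AE or SAE as applicable". Section 8.3.12 adds, for a death from an event that began after that period, that if "the event is considered to be due to a late onset toxicity to study drug, then it should also be reported as an SAE".

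**Tabulation, protocol.** Section 9.4.2.1 puts AEs more than 90 days after stopping study drug in their own listing and states: "These events will not be included in AE summaries". It makes no exception for related, serious or fatal events.

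**Tabulation, SAP.** Section 4.2.5.1 ends the AE summary tables at 90 days after treatment or at first subsequent anticancer therapy, whichever is earlier. Some tables are repeated without the subsequent-therapy cut, but these also stop at 90 days. The exclusion of later events is repeated with a proviso that allows stated exceptions. One exception appears in the list of tables by system organ class and preferred term: "AEs which started prior to first dose or after 90 days following date of last dose".

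**Deaths, SAP.** The first death summary counts all deaths whatever their date. One of its rows is "Death after end of safety follow up period", restricted to deaths not due to the disease.

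**The concern.** After day 90 the plan asks sites for one kind of event: one judged to be caused by study drug. These are the events a reader would look for in the counts of related SAEs, related fatal AEs and AEs of special interest, yet the windows of those tables exclude them.

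The separation also runs the wrong way. AEs between first subsequent therapy and day 90, some of which the SAP regards as likely due to that therapy, get their own table. Late drug-attributed AEs share a table with pre-dose AEs. Pre-dose AEs are collected from part II consent, in participants whose chemoradiation ended 1 to 28 days before the first dose (part II inclusion criterion 5), so that table may hold many events unrelated to durvalumab.

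At stake is whether a reader of the study report can count, by arm, the late serious and fatal events attributed to study drug. SAP 5.1.2 describes IDMC safety review as running until the final PFS analysis, while survival follow-up continues. The reported tables therefore carry more weight for events that arise later.

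**Working it through.** The documents state no figure to reproduce, so the check traces one case through the outputs: an SAE that starts more than 90 days after the last dose and is judged related to study drug.

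| Output | Is the case included? | Can it be identified as late and related? |
|---|---|---|
| Listings of all AEs and of AEs after 90 days (protocol 9.4.2.1; SAP 4.2.5.1) | Yes | Yes, line by line: the SAP listing of all AEs carries the investigator's relationship assessment |
| Related AEs, related SAEs, related fatal AEs (SAP 4.2.5.1) | No: the general window applies and no exception is stated | Not applicable |
| AESI/AEPI summaries (SAP 4.2.5.1) | No: same reason | Not applicable |
| imAE summaries (SAP 4.2.5.1) | Probably not: same manner as AESI/AEPI, but the derivation rules are in the imAE charter, which is not available here | Not applicable |
| Table of AEs before first dose or after 90 days (SAP 4.2.5.1) | Yes, by arm, system organ class and preferred term | No: pooled with pre-dose AEs, and no split by causality, seriousness, grade or outcome is stated |
| Death summary, if fatal (SAP 4.2.5.1) | Yes, in total deaths and in a cause row | No: no row shows attribution to study drug |

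The row in which a fatal case would fall is not fixed by the text. It fits the row for deaths after safety follow-up that are not due to the disease. It could also fit the row for deaths with a fatal AE and no disease cause. That row has a sub-row limited to onset within 90 days or before subsequent therapy, which suggests that the parent row is wider.

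**Protocol against SAP.** Protocol 9.4.2.1 keeps both pre-dose and post-90-day AEs out of summaries, while SAP 4.2.5.1 tabulates both. SAP Section 6, on changes from the protocol, does not mention this. SAP 3.3.1 describes AE collection as ending at 90 days and does not refer to the late-onset rule.

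**Scale of one omitted participant.** No rate of late events is given, so only the weight of a single case can be worked out. With about 400 randomised 2:1, and assuming that all are treated:

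- durvalumab: 400 × 2/3 ≈ 267, so one participant is 1/267 = 0.37 percentage points;
- placebo: 400 × 1/3 ≈ 133, so one participant is 1/133 = 0.75 percentage points.

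A participant who already has an in-window event in the same table adds nothing to its overall count.

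**The case against.** The strongest reply is that nothing is hidden and the cut-off is reasonable.

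- Both documents require a listing of AEs after 90 days, and the SAP listing of all AEs gives each event's relationship to study drug. AESI/AEPI are listed, with fatal ones listed again. If late cases are few, the listings show every one. This stands, but a listing leaves the reader to do the counting.
- Routine collection ends at day 90, and protocol 8.3.2 does not oblige investigators to seek events in former participants. Protocol 6.2.4 allows unblinding at the investigator's request after study drug has stopped and progression plus the follow-up scan is recorded, and SAP 5.1 says the study is unblinded at the primary PFS analysis. Late attribution may therefore be both unsystematic and unblinded. This stands in full. It is a reason to keep late events out of the 90-day tables, but not a reason to pool them with pre-dose AEs.
- Safety is descriptive, and SAP 4.2.5 allows additional summaries. This limits the consequence, but an optional summary is not a planned one.

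A reader might infer more than the text supports:

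- *That late toxicities are barred from every summary.* This fits the protocol sentence alone; the SAP counts them in one table.
- *That late fatal toxicities are lost.* They are in the total of all deaths and in a cause row.
- *That the safety contrast is biased in favour of durvalumab.* The documents give no rate by arm, and late reports are not comparable with systematic 90-day data.
- *That the protocol expects late immune effects.* Sections 8.3.2 and 8.3.12 are conditional reporting rules, and the risk and AESI sections (2.3.2, 8.3.13) state no such expectation.

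**Conclusion.** The point holds as a gap in presentation. Late-onset events judged related to study drug must be reported, but as the plan is written they enter no related-SAE, related-fatal-AE or AESI/AEPI count. They are listed, counted in one pooled table, and included in the death summary without attribution. The same probably applies to imAE counts, but that depends on the imAE charter.

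The size of the undercount is unknown and may be zero. The conclusion rests on reading the SAP's general 90-day window as governing every AE table with no stated exception, and on table titles alone, since no table shells are available. Efficacy, type I error and the 90-day safety tables are unaffected. The change is a cheap improvement that would make late serious and fatal drug-attributed events countable by arm.

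**What to change.** 1. Leave the existing 90-day tables unchanged.
2. In SAP 4.2.5.1, split the pooled table in two: AEs starting before the first dose, and AEs starting more than 90 days after the last dose.
3. Add a separate by-arm summary of the late AEs judged related to study drug, with rows for any, grade 3 or higher, serious, fatal, and AESI/AEPI/imAE. Confirm against the imAE charter how late events are classified.
4. In the death summary, show whether each death after the safety follow-up period was attributed to study drug, and state which row a fatal late AE belongs to.
5. Align protocol 9.4.2.1 with SAP 4.2.5.1, or record the difference in SAP Section 6.

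The cost is one split table, one short summary and a few rows, all from data already collected. The drawback is that the late counts rest on unsystematic capture and possibly unblinded attribution. They should carry a footnote saying so and should not be added to the 90-day counts.

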9.4.2.2 Safety assessments

For the change from baseline summaries for vital signs, laboratory data, ECGs, and physical examinations, the baseline value will be the latest result obtained prior to the start of study treatment.

The QTcF will be derived during creation of the reporting database using the reported ECG values (RR and QT) using the following formula:

 $QTcF = QT/RR^{(1/3)}$ where RR is in seconds

Corrected calcium product will be derived during creation of the reporting database using the following formula:

Corrected calcium (mmol/L) = Total calcium (mmol/L) + ($[40 - \text{Albumin} (G/L)] \times 0.02$)

The denominator used in laboratory summaries will only include evaluable participants, ie, those who had sufficient data to have the possibility of an abnormality.

For example:

- If a CTCAE criterion involves a change from Baseline, evaluable participants would have both a pre-dose and at least 1 post-dose value recorded.
- If a CTCAE criterion does not consider changes from Baseline to be evaluable, the participant need only have 1 post-dose value recorded.

The denominator in vital signs data should include only those participants with recorded data.

9.4.3 Calculation or derivation of patient-reported outcome variables

All PRO questionnaires will be scored according to published scoring guidelines or the developer's guidelines, if published guidelines are not available. All PRO analyses will be based on the mITT (primary population), and separately on the ITT population.

9.4.3.1 EORTC QLQ-C30 and QLQ-LC13

Symptoms and overall quality of life will be assessed using EORTC QLQ-C30 and QLQ-LC13 (secondary endpoints).

The EORTC QLQ-C30 consists of 30 questions that can be combined to produce 5 functional scales (physical, role, cognitive, emotional, and social), 3 symptom scales (fatigue, pain, and nausea/vomiting), 5 individual items (dyspnoea, insomnia, appetite loss, constipation, and diarrhoea), and a global measure of health status. The QLQ-LC13 is a lung cancer-specific module from the EORTC for lung cancer comprising 13 questions to assess lung cancer symptoms (cough, haemoptysis, dyspnoea, and site-specific pain), treatment-related symptoms (sore mouth, dysphagia, peripheral neuropathy, and alopecia), and pain medication. With the exception of a multi-item scale for dyspnoea, all are single items. The dyspnoea scale will only be used if all 3 items have been scored; otherwise, the items are treated as single-item measures.

An outcome variable consisting of a score from 0 to 100 will be derived for each of the symptom scales/symptom items, the functional scales, and the global health status/QoL scale according to the EORTC QLQ-C30 Scoring Manual (EORTC QLQ-C30 Scoring Manual, Third Edition) and EORTC QLQ-LC13 instructions.

Higher scores on the global health status/QoL and functioning scales indicate better health status/function, but higher scores on symptom scales/items represent greater symptom severity. Changes in score compared with baseline will be evaluated. For each subscale, if <50% of the subscale items are missing, then the subscale score will be divided by the number

of non-missing items and multiplied by the total number of items on the subscales (Fayers et al 2001). If at least 50% of the items are missing, then that subscale will be treated as missing. Missing single items are treated as missing. The reason for any missing questionnaire will be identified and recorded. If there is evidence that the missing data are systematic, missing values will be handled to ensure that any possible bias is minimised.

Definition of clinically meaningful changes

Changes in score compared with Baseline will be evaluated. A minimum clinically meaningful change is defined as an absolute change in the score from Baseline of ≥ 10 for scales/items from the EORTC QLQ-C30 (Osoba et al 1998). For example, a clinically meaningful improvement in physical function (as assessed by EORTC QLQ-C30) is defined as an increase in the score from Baseline of ≥ 10 , whereas a clinically meaningful deterioration is defined as a decrease in the score from Baseline of ≥ 10 . At each post-baseline assessment, the change in symptoms/functioning from Baseline will be categorised as improvement, no change, or deterioration, as shown in Table 12 in Section 9.4.3.3.

Time to symptom deterioration (QLQ-C30 and QLQ-LC13)

Time to deterioration in symptoms, functioning and global health status/QoL will be evaluated, more details will be specified in the SAP.

Symptom improvement rate (QLQ-C30 and QLQ-LC13)

The symptom improvement rate will be defined as the number (%) of participants with 2 consecutive assessments, at least 14 days apart, that show a clinically relevant improvement (a decrease ≥ 10) in that symptom from Baseline.

The denominator will consist of a subset of the mITT/ITT who have a baseline symptom score of ≥ 10 .

QoL/function improvement rate (QLQ-C30)

The QoL/function improvement rate will be defined as the number (%) of participants with 2 consecutive assessments, at least 14 days apart, that show a clinically relevant improvement (an increase score ≥ 10) in that scale from Baseline.

The denominator will consist of a subset of the mITT/ITT who have a baseline QoL/function score of \leq 90.

CHANGE FROM BASELINE

Change from baseline in key symptom scores of dyspnea, cough, chest pain, fatigue and appetite loss will be analysed using a mixed model for repeated measures (MMRM) analysis.

9.4.3.2 Calculation or derivation of patient-reported health state utility (EQ-5D-5L)

The EQ-5D-5L index comprises 5 dimensions of health (mobility, self-care, usual activities, pain/discomfort, and anxiety/depression). For each dimension, respondents select which statement best describes their health on that day from 5 possible options of increasing levels of severity (no problems, slight problems, moderate problems, severe problems, and unable to/extreme problems). A unique EQ-5D health state is referred to by a 5-digit code allowing for a total of 3125 health states. For example, state 11111 indicates no problems on any of the 5 dimensions. These data will be converted into a weighted health state index by applying scores from EQ-5D value sets elicited from general population samples (the base case will be the United Kingdom valuation set, with other country value sets applied in scenario analyses). Where value sets are not available, the EQ-5D-5L to EuroQoL 5-dimension, 3-level health state utility index crosswalk will be applied (van Hout et al 2012, van Reenen and Janseen 2015). In addition to the descriptive system, respondents also assess their health on the day of assessment on a visual analogue scale, ranging from 0 (worst imaginable health) to 100 (best imaginable health). This score is reported separately.

